---

## Scientific Title

Paint the pain: Investigating the biopsychosocial impacts of a guided self-reflective visual art creation program on individuals living with chronic pain- a pilot randomised controlled trial

## Simplified Title

Paint the pain

## Aim

To investigate the physiological, psychological and social impacts of visual arts creation in individuals living with chronic pain

## Hypothesis

Creation of visual art produces physiological, psychological and social benefits for individuals living with chronic pain.

## Sub-hypotheses

1. That the intervention will have a priming effect on clinically guided pain management which will follow this project. The clinical process involves a lot of reflection on the circumstances that impact on participants' pain, and we hypothesise that some of this reflective work will begin through the process of visual art creation.
2. That participants will describe visual art creation as beneficial in one or more dimensions of the 'CHIME' framework –Connectedness, Hope, Identity, Meaning in life and Empowerment (Jensen, 2018; Piat, Seida, & Sabetti, 2017).

## Background

People living with chronic pain experience a multitude of feelings including anxiety, anger, depression, shame, self-loss, identity disruption, and isolation, all of which heighten their distress. A recent study showed that the median waiting time to be admitted to a publicly funded pain management service is 150 days in Australia. That is 5 months of waiting in pain, demonstrating pain management services are currently unable to meet service requirements adequately. Therefore, while current pain services deliver pain interventions, there is a need for programs targeting the distress and isolation associated with waiting in pain, and community options for support and social engagement of individuals with chronic pain, for the long-term.

Creation of visual arts is amongst the highest of human cognitive achievements. Visual arts convey emotions, concepts, ideas, cultural differences and overcomes language limitations. Studies investigating the impacts of visual arts on psychosocial and physiological effects in different clinical populations have demonstrated that the application of arts is associated with effects on well-being such as improvements in overall health, loneliness, self-awareness (Geue et al., 2010) and morale (Cohen et al., 2006), and clinical benefits of reduced healthcare utilisation. Further, physiological benefits include improvements in heart rate, blood pressure (Leckey, 2011), and cortisol levels in clinical populations (Clow A, 2006). Finally, at the neural level, visual art production has been observed to enhance functional connectivity of the default mode network in the brain (Bolwerk, Mack-Andrick, Lang, Dorfler, & Maihofner, 2014). This network is associated with cognitive processes such as self-examination, reflection, prospection, autobiographic memory, and understanding of the emotional states and intentions of others (Gusnard, Akbudak, Shulman, & Raichle, 2001; Raichle, 2010).

Despite the potential benefits for individuals with chronic disability, there is limited information on the impacts of visual arts on patients with chronic pain (Kirkham, Smith, & Havsteen-Franklin, 2015; Mische Lawson et al., 2012). Using art therapeutically, as well as a 'primer' for patients on waiting lists for pain management programs, is a novel means of providing them with an outlet for their pain-related distress, anxiety and feelings of social isolation. At the same time, art can provide a means to boost the therapeutic alliance and support patients to communicate their pain and re-establish connections with their community. In addition, this project proposes to explore how visual arts can be used as a medium to help develop the therapeutic alliance by enabling people in pain to express and communicate their pain experience during the therapeutic encounter.

Therefore, this pilot study aims to investigate a) the physiological, psychological and social impacts of visual arts creation in participants with chronic musculoskeletal pain and b) To evaluate how creation of visual arts can be used as a medium to enable people in pain to express and communicate their pain experience during a therapeutic encounter.

# Research Plan

## Study Type

A pilot randomised controlled trial

## Setting/Location

This project will be run in partnership with the Prince Alfred Hospital (RPAH) Pain clinic as the recruitment site and the Art Gallery of NSW (AGNSW) as the intervention site.

## Duration of Study

One year

## Methods

### *Study Population*

Patients (>18yrs) with chronic musculoskeletal pain (persistent pain >3 months) and on the waiting list of the pain management program at RPAH pain clinic will be the population of interest.

### *Recruitment*

Participants will be recruited from the waiting list of the pain management program at the RPAH Pain Management Clinic. RPAH Pain Management Clinic routinely delivers a one-day introductory program (STEPS), once a month for patients waiting to commence a pain management program. At the end of the STEPs session, information regarding the “Paint the Pain” project will be provided to patients by a research assistant and an artist from the AGNSW. Patients who are interested to receive further information will be asked to provide their contact details (email and phone number) and will be contacted by our research assistant.

All prospective participants will be provided with the ethically approved participant information sheet and given ample time to read and ask any questions they have about participation. The project research assistant will also contact participants by phone/email to provide detailed information about the project, research process, and participation requirements and answer any questions they may have and check their eligibility against the inclusion criteria.

The details of our recruitment strategy are provided in Appendix 1.

### *Key inclusion criteria*

Individuals above the age of 18, who have been diagnosed with chronic musculoskeletal pain, whose pain has been stable over the past 3 months will be included in this study.

### *Key Exclusion Criteria*

Individuals who have started any new pain-related medications within 3 months prior to recruitment will be excluded from the study.

### *Consent*

To be included in the study, each participant will need to provide written informed consent. Participation will be voluntary, and participants can withdraw at any time. signing the consent form, they will be randomised to either the intervention group or control group.

### *Randomisation*

The Participant Information Statement and Consent form will be emailed to participants who meet the inclusion criteria. The project research assistant will then contact participants by phone to provide detailed information about the project, research process, and participation requirements and answer any questions they may have.

People who agree to participate by signing the consent form will be randomised to either the intervention group or control group. Our randomisation approach will be impacted by the number of participants recruited from the STEPs Program.

- If we are successful in recruiting 20 patients after attending one of the monthly STEPs programs, participants will be randomly allocated by the research team to either intervention or control group, using a computer-generated sequence and a 1:1 allocation ratio.
- If we are not successful in recruiting 20 patients from one STEPs program, we aim to use the quasi-randomisation approach. That is, the first group of participants recruited from the first STEPs program will be allocated to the intervention group and participants recruited from the next STEPs program will be allocated to the control group.

This approach will not extend the waiting time of patients to receive their pain assessment and treatment, should we not succeed in recruiting 20 participants via the first STEPs program.

Participants will be notified by phone/email of their group and intervention participants will be notified about their first session of art observation and creation at the Art Gallery of NSW.

### *Study Procedure*

After receiving consent, participants will be randomised into an intervention or a control group. The intervention group will undergo a five sessions of art intervention. The assessments will take place in both groups at baseline, at post intervention (at conclusion of 5 sessions), 3 months, 6 months and 12 months' time points. In addition, several measurements will be

collected throughout the intervention sessions including saliva samples, pain behaviour using a pain diary, and heart rate using a mobile app. For the control group, the treatment will be as usual (they will be on the waitlist to receive their pain treatment), and they will be offered two tickets to visit the art gallery and art creation tool kit, once the study is concluded.

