### *Endpoints/Outcome Measurements*

#### *Quantitative Approach*

To assess patient demographics and pain-related medical history, we will seek participants' permission to access the results of their ePPOC questionnaires (electronic Persistent Pain Outcomes Collaboration, Appendix 2). These questionnaires are required as part of admission to the pain management programs in Australia. After gaining informed consent, previously completed ePPOC questionnaires will be accessed and recorded. We briefly provide information on the items extracted from ePPOC data. For detailed information, please refer to Appendix 2. We will extract the following items from ePPOC questionnaires:

1. Patient demographic information:

In ePPOC analysis and reporting, patient information defines the patient population and contextualises the patient outcomes. We will record: sex, age, height (cm), weight (kg), postcode, and country of birth.

2. Pain History:

- *Episode information:* An episode is defined as a continuous period of care for a patient in one pain management service. Under this definition, a patient may have more than one episode. For example, a patient may receive treatment for pain at more than one pain management service or be re-referred to a service following completion of a previous episode. There should however, be only one active episode at any one time for a patient at a pain management service.

The information collected at the episode level reflects the circumstances at the beginning of the episode. We will record Patients' referral date for the current pain episode, episode start date, episode start mode (how the episode began), cause of pain, pain duration (the length of time for which the patients' pain has been present, comorbidities (comorbid conditions the patient has at the start of the episode of care).

---

 ePPOC is a program which aims to help improve services and outcomes for individuals experiencing chronic pain through benchmarking of care and treatment.

- *Pathway information:* The “Pathway” describes the type of treatment the patient receives/has received during the episode of care. Pathways generally begin after education/orientation programs and appointments designed to assess the patient and determine the most appropriate treatment pathway. There are four primary pathways:
  - Pathway 1 Group pain management program(s) (PMP)

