### 3. Patient reported outcome measures:

As part of ePPOC, standardised patient questionnaires are completed by the patient in ‘referral’ and ‘follow-up’ questionnaires at:

- initial referral to the pain management service;
- the beginning and end of each pathway within an episode; and
- follow-up three to six months after the end of the episode.

While we will use the recorded data from ePPOC, we will also assess and record following outcome measures at commencement and at the end of our art intervention in both groups. Patient reported outcome measures are:

- *Pain description:* Patient is asked to choose or describe the following items:
  - Frequency of their pain (e.g., always present, occasionally present, etc).

- Pain site: report of where on a body map the patient feels pain.
  - Pain severity: The patient is asked to rate the intensity of their pain at its worst in the last week, at its least in the last week, on average, and right now. For each of the four questions above, the patient rates their pain on a scale of 0 to 10, where 0 = 'No pain' and 10 = 'Pain as bad as you can imagine'.
  - Rating of their change-overall (on a scale of -3 to 3 where -3 is 'very much worse', 0 is 'unchanged' and '3' is 'very much better'.)
  - Rating of their change-physical abilities (on a scale of -3 to 3 where -3 is 'very much worse', 0 is 'unchanged' and '3' is 'very much better'.)
  - Pain interference: The patient is asked to rate how much their pain has interfered with the following in the past week: general activity, mood, walking ability, normal work (both outside the home and housework), relations with other people, sleep, enjoyment of life. For each of the seven questions above, the patient rates their pain on a scale of 0 to 10, where 0 = 'Does not interfere' and 10 = 'Completely interferes'. An average rating of pain interference is calculated by summing the scores for the seven questions above, divided by the number of questions the patient completed. If more than one number has been circled for a question, use the highest score.

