#### *Statistical Considerations/Data analysis (Quantitative)*

Statistical support will be sought from the Faculty of Health Sciences Biostatistician ([name]). Descriptive statistics will be used to describe the population, patient-reported outcome measures and physiological outcome measures. Data will be assessed for normality. Generalized linear models will be used to compare the mean change in outcomes (continuous variables) from baseline to each time point between the intervention and control groups. This will provide effect estimates and 95% confidence intervals for any difference between the intervention and control group.

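### As written, the study's own baseline questionnaires fall after participants know their group, so a passing reaction to allocation can bias the between-group comparison of change.

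*Protocol*

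**What the plan says.** The relevant statements are spread over several sections of the protocol.

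- **Allocation follows consent.** Randomisation: "People who agree to participate by signing the consent form will be randomised to either the intervention group or control group". Study Procedure repeats it: "After receiving consent, participants will be randomised into an intervention or a control group". The Consent section says the same. None of them puts an assessment between the two steps.
- **Disclosure.** Randomisation: "Participants will be notified by phone/email of their group and intervention participants will be notified about their first session". Both arms learn their group, and the intervention arm hears about its first session in the same step.
- **Timing of self-reports.** Patient reported outcome measures: "we will also assess and record following outcome measures at commencement and at the end of our art intervention in both groups".
- **Schedule.** Study Procedure: "The assessments will take place in both groups at baseline, at post intervention (at conclusion of 5 sessions), 3 months, 6 months and 12 months'". Baseline is listed but is not placed relative to randomisation or notification.
- **Analysis.** Statistical Considerations (Quantitative): "Generalized linear models will be used to compare the mean change in outcomes (continuous variables) from baseline to each time point", between the two groups.
- **Earlier data.** Quantitative Approach: "previously completed ePPOC questionnaires will be accessed and recorded". These contain the same instruments, but no section says they serve as the analysis baseline.

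**The concern.** Pain severity, pain interference, DASS21, PSEQ and PCS are all self-reported by people who know their group. They were recruited at a session where a gallery artist helped present the project, so being told that they will or will not attend may matter to them. Disappointment or anticipation could move mood, catastrophising or self-efficacy scores before the first study questionnaire is completed.

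A baseline measured after disclosure is no longer certain to be balanced by the allocation, yet the planned comparison subtracts it. A temporary shift in one arm's baseline then appears as a between-group difference in change. In addition, a participant who leaves on learning their group contributes no study-collected change score, and such losses may differ between arms. The Outcomes section intends the pilot to inform the choice of outcome measures and sample sizes for later studies, so a distorted contrast could carry forward.

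**Working it through.** **Step 1: the order of events.** The sequence below combines the sections cited above.

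1. Consent signed (Consent; Randomisation; Study Procedure).
2. Allocation to a group (same sections).
3. Participants told their group, with notice of the first session for the intervention arm (Randomisation).
4. Study questionnaires at the start of the art program, in both arms (Patient reported outcome measures).
5. Change from baseline compared between arms (Statistical Considerations).

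Step 3 has to precede the first session, because it announces that session. Step 4 is tied to the start of the program. So step 4 follows step 3 unless some other section moves it earlier, and none does.

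**Step 2: what a shift would do.** The protocol gives no SD, effect size or correlation, so there is no figure of its own to reproduce. The inputs below are assumptions, except the arm size: 20 participants at 1:1 gives 10 per arm (Randomisation).

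Let one arm's reported baseline move by d (in SD units) because of the allocation news. Let the shift be gone at follow-up, let there be no true effect, and let the baseline–follow-up correlation be ρ with equal variances.

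- Change score: size of bias = d.
- Baseline-adjusted model: the slope is ρ, so size of bias = ρ × d.
- SE of the change contrast = √(2(1 − ρ)) × √(2/10). At ρ = 0.5 this is 1.000 × 0.447 = 0.45 SD; at ρ = 0.7 it is 0.775 × 0.447 = 0.35 SD.

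The type I error comes from 200,000 simulated trials per setting, with a two-sided 5% t-test on change.

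| d (assumed) | Bias, change score | Bias, adjusted, ρ = 0.5 | Bias, adjusted, ρ = 0.7 | Type I error on change, ρ = 0.5 | Type I error on change, ρ = 0.7 |
|---|---|---|---|---|---|
| 0.2 | 0.2 | 0.10 | 0.14 | 7% | 9% |
| 0.3 | 0.3 | 0.15 | 0.21 | 10% | 13% |
| 0.5 | 0.5 | 0.25 | 0.35 | 19% | 28% |

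Adjustment reduces the bias to a fraction ρ of the shift but does not remove it.

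**Step 3: direction and persistence.** If controls score worse, or intervention participants better, at baseline only, the change contrast is biased against the intervention. The opposite reactions bias it in favour. If a fraction k of the shift remains at follow-up, the change-score bias is (1 − k) × d, which is zero at k = 1.

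**Step 4: withdrawals.** With 10 per arm, each participant lost between notification and the first questionnaire removes 1/10 of that arm from the study-collected change analysis.

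**The case against.** The strongest reply is that no single sentence states this order. Study Procedure lists a baseline without placing it, and the reference to the start of the program is mainly a list of instruments. That is fair: the sequence is inferred. The inference is nevertheless the natural one, and nothing in the protocol points to an earlier baseline.

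Second, pre-allocation data exist. The ePPOC questionnaires begin at referral and cover the same measures, so someone who withdraws after notification may still have an earlier score. A reader might infer that such a person has no baseline of any kind, and the documents do not support that. But ePPOC scores are tied to referral and pathway points, may be old, and are not designated as the analysis baseline. A separate SAP could choose between the scores. It could not move a study questionnaire to before disclosure.

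Third, the reaction may be small. Both arms are already on the clinic's waiting list, so the news for controls is that they will not attend the art program, not that a new wait begins. DASS21, pain interference and most pain ratings ask about the past week, which may dampen a brief response. However, the present-pain rating and the PSEQ ask about the present, and the protocol does not give the interval between notification and the first questionnaire.

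Finally, this is a pilot of about 20 people. That limits how much weight any contrast can bear, but the correction is cheap whatever the sample size.

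**Conclusion.** The concern stands as a correctable weakness in the order of trial conduct. Read together, the sections place the study-collected baseline questionnaires after participants know their group, and the between-group comparison of change relies on that baseline.

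Three stronger readings are tempting and should be resisted:

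- **That the baseline is contaminated.** The documents show only that it can be. Size and direction are unknown, and a shift that lasts to follow-up cancels in the change score.
- **That every analysis is affected.** The point concerns the between-group comparison of change in continuous outcomes. The descriptive and qualitative analyses do not rest on it.
- **That the figures estimate a bias in this trial.** They rest on an assumed shift of 0.2 to 0.5 SD that fades completely and an assumed correlation of 0.5 or 0.7. At 0.2 to 0.3 SD the bias is 0.2 to 0.3 SD on the change score, against a standard error of 0.35 to 0.45 SD. That would be a sizeable part of the random error, though smaller than it.

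**What to change.** In Randomisation, Study Procedure and Patient reported outcome measures (and in Consent, which repeats the trigger), state one order for both arms: consent, baseline questionnaires completed and logged, randomisation, notification. Release the allocation only once the completed baseline is logged.

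Under the fallback that allocates by STEPs cohort there is no randomisation to precede. There, require the baseline to be completed before participants are told, or can otherwise learn, their group. This does not address the fallback's other weaknesses.

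State that this pre-allocation score, and not the earlier ePPOC score, is the analysis baseline.

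Saliva and heart rate may stay at their session-linked times. The protocol ties them to the art sessions and matches control sampling to the time of day, so moving them would probably need an extra contact.

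The cost is a small logging step and a slightly longer gap between baseline and the first session. The sample size does not change. With the baseline completed before disclosure, the allocation-driven baseline shift is zero by design, and so is the bias from this source in the questionnaire outcomes.

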### *Study intervention*

Participants randomised/allocated to the art intervention group will be asked to attend five sessions of art observation and creation at the Art Gallery of NSW (3hrs per session, 1 session per week) for over five weeks. To monitor adherence, participants will be contacted by our research assistant two days prior to the session and will be sent a text message requesting to confirm their attendance 24 hours prior to the session.

The first hour of the session, will be allocated to observation and discussion of 3 art works at the art gallery of NSW. This session will be guided by two artists at the gallery.

The second hour of the session is allocated to creation of the art works guided by an artist, and two researchers experienced in the field of arts and health, and a rehabilitation counselling researcher. During these sessions, participants will be guided to explore and communicate their pain experiences through the creation of visual artworks including each individual's pain and its impact on their well-being, personal and social life. Participants may also depict their 'ideal' self and life if they could 'tame' their pain. Participants will be guided to share and discuss these art creations and experiences with family, others with chronic pain, and with community members. The themes for the five art making sessions will be decided upon iteratively by the research team from the following list:

1. Express your pain in paint. Explore any of its dimensions.
2. Paint yourself with your pain in your present life.
3. Paint the self you hope to be/ you could be in relation to moving beyond pain /taming pain
4. Paint all the places the pain has come from or are connected with
5. What do you need most in order to live with pain?
6. Paint your future self and how you would like to live
7. Paint what is meaningfully connected to your pain – in any way.

The final hour of the art-making sessions will be a group discussion and reflection on the art creation process, effectively a group interview, conducted jointly by team members, a rehabilitation counsellor and a qualitative arts and health researcher. This group interview is similar to a 'focus group' and is understood partly as 'action research' in which reflections prompted by the discussion may influence their experiences in the subsequent session.

